4. SELECTION AND ENROLLMENT OF PARTICIPANTS

Study staff will screen, recruit and randomized n=290 eligible diverse participants distributed participants aged 40 to 65 yr for this project from Co-op City or adjacent communities, a diverse cooperative housing development designed to provide affordable housing in the northeast section of Bronx County. Co-op City’s size (>50,000 residents), diversity (60.5% African American, 27.7% Hispanic), median age (42 years), income (\$50,900) and proximity to the Einstein Medical complex make it an ideal population center from which to recruit a representative sample. Additionally, as residents have ownership rights to their unit, turnover of residents in

this housing complex is low. The staff will recruit the target sample and implement methods to maximize participation and retention based on Mody et al., 2008 (66). To minimize selection bias, we will use telephonic recruitment methods that have been developed and validated for use in the Einstein Aging Program Project (NIA P01AG003949) since 1993. These procedures consist of obtaining Registered Voter Lists (RVL) from the New York City Board of Elections for the Co-op city zip code, which define a sampling block covering more than 90% of individuals listed in U.S. Census tabulations for that area. Individuals on the RVL will be categorized into 10-year age intervals and assigned to age, race and gender sampling stratified sampling blocks. Letters of introduction will be sent to members of each sampling block, explaining the project and its goals, how the recipient of the letter was identified, and that they will be contacted by telephone within two weeks. The letter includes a telephone number for individuals to call if they do not wish to be contacted by telephone; all individuals doing so will be removed from the sampling blocks. During the recruitment call recruiters will establish rapport, identify exclusions and screen for basic computer use skills. Interested and eligible individuals will then be enrolled.

4.1 Inclusion Criteria

Eligibility criteria for the study will include:

- Living, working, visiting (e.g. for shopping, doctors' visits, etc.) or attending school in Co-op City, Bronx or adjacent communities and between 40-65 yr of age
- Willing to participate in study for 27 months
- willing to track food intake
- employment that does not interfere with ability to respond to prompts (for example a shift worker who needs to tend to patients may not be a good candidate)
- willing to accept either study condition (comparison or intervention)
- willing to participate in a study where weight loss is not a primary goal
- participant with controlled hypertension
- access to a smartphone that can work with any HTML5 compliant web browser to enter food records.
- reliable access to the internet

4.2 Exclusion Criteria

Exclusion criteria for the study will include:

- history of neurologic condition or disease producing cognitive dysfunction
- history of traumatic brain injury; current psychiatric disorder known to significantly affect cognition (e.g., active major depression, history of eating disorders, active PTSD)
- participants with type 2 diabetes who are on medications that cause hypoglycemia (e.g. insulin, sulfonylureas, and meglitinides) and who have had hypoglycemic episodes
- previous history of cardiovascular disease (CVD): myocardial infarction, heart failure, stroke (that affects physical functioning), hospitalization for CVD event or procedure.
- uncontrolled hypertension defined as blood pressure $\geq 140/90$ mm Hg
- participant primarily interested in weight loss as judged by discussion with participant and any severe chronic illness

- low literacy or other medical or other conditions such as pregnancy or breastfeeding that would preclude completion of study activities
- history of alcohol or drug dependence
- hematologic disease or malignancy not in remission for 5 years or more
- visual, auditory, or motor impairment that precludes cognitive testing.
- participating in weight loss programs such as: Weight Watchers', Atkins or extreme dieting programs
- participating in programs that enhance cognition such as playing brain games
- taking medications that impact cognition such as Aricept
- diagnosis of kidney/renal disease on dialysis or special diet
- diagnosis of liver disease
- Using Continuous Positive Airway Pressure (CPAP) and experiencing disrupted sleep

4.3 Study Enrollment Procedures

To minimize selection bias, we will use telephonic recruitment methods that have been developed and validated for use in the Einstein Aging Program Project (NIA P01AG003949) since 1993. These procedures consist of obtaining Registered Voter Lists (RVL) from the New York City Board of Elections for the Co-op city zip code, which define a sampling block covering more than 90% of individuals listed in U.S. Census tabulations for that area. Individuals on the RVL will be categorized into 10-year age intervals and assigned to age, race and gender sampling stratified sampling blocks. Letters of introduction will be sent to members of each sampling block, explaining the project and its goals, how the recipient of the letter was identified, and that they will be contacted by telephone within two weeks. The letter includes a telephone number for individuals to call if they do not wish to be contacted by telephone; all individuals doing so will be removed from the sampling blocks. During the recruitment call recruiters will establish rapport, identify exclusions and screen for basic computer use skills. Interested and eligible individuals will then be enrolled.

The recruitment phase consists of the following:

- Letter of Introduction to the study (see appendix) is sent to individuals
- After 7-10 days of the letter being sent, attempt to reach the individual by phone.
- If contact is made with the individual, oral consent is obtained to proceed with the telephone interview (see appendix IRB oral consent).
- Telephone screen will be administered to determine eligibility

During the recruitment phase, recruiters will complete an entry in a Screening Log for each in the sampling block. The Screening Log will contain the following information:

- # of phone attempts to reach the individual
- Whether the individual was reached
- Whether the individual agreed to a phone interview
- If they agreed to phone interview, were they eligible
- If not eligible, reason for ineligibility

In addition to telephonic methods, we will attend community events (fairs, events at local malls and businesses) and also use email blasts, ResearchMatch newspaper articles and distribute flyers to recruit participants. We will recruit from the Montefiore Medical Group in Co-op City (Bartow) for participants who live, work, visit (for shopping, doctor's appointments) attend school in Co-op City or neighboring communities and will also use electronic medical records from the Montefiore Medical Group in these communities to create recruitment lists that we will use to contact participants. Our recruiter will describe study to participants in waiting area and provide contact information about the study or sign up interested participants. Flyers will be provided. Physicians in the practice may also provide flyers about study to participants and refer them to study recruitment phone line or email address.

Once it has been determined that an individual is eligible to participate and he/she agrees, an appointment is made for two screening visits. At these visits, participants perform run-in such as using the smartphone for assessing cognition and mood and also learn to track foods using the smartphone. They are also given home assignments to assess ability to perform the study tasks. Randomization occurs after screening visit #2 when participants return to the clinic with the smartphones and are judged to be eligible to proceed to study activities.

The tasks at each visit are outlined below:

5 **STUDY INTERVENTIONS**

5.1 **Interventions, Administration, and Duration**

If assigned to the Multicultural Healthy Diet, participants will:

- follow an anti-inflammatory healthy dietary pattern over the 27 month duration of the study
- attend four 1-2 hour groups sessions on shopping & cooking healthy diet in the first 2 months at Co-op City or other convenient location (up to 8hr)
- write down foods eaten 3 times/month for 18 months (18 hr)
- receive 16 monthly 20 minute phone calls and/or online program materials from coaches on following diet after the group sessions end; for participants who are difficult to reach, up to three sessions can be completed in one phone call (5 hr, 20 minutes)

Dietary Component of the Intervention: This will be a small group intervention with tailored phone calls after the core sessions. Participants will undergo an 18 month intervention (four semi-monthly small group sessions for 2 months followed by monthly phone calls for 16 months). The small group sessions will last 2 hours for 3-4 participants. Monthly phone calls last 20 minutes and are focused on dealing with specific challenges such as dealing with social situations, eating at fast food outlets. The intervention will be hands-on and delivered using a motivational interviewing approach and include a visit to the supermarket in session 2 with the small group format, with a focus on structuring one's own environment to maximize adherence to the study. While some participants may lose a small amount of weight on this diet (see

example in Figure 6), weight loss is not a primary goal and dietary intake will be reviewed as eucaloric and have the following distribution of macronutrients: 33% fat, 38-41% carbohydrate and 26% protein, (may vary as MHD is individualized). The core sessions (Table below) are:

1. Key components of the MHD Diet & Hit List
2. Shopping Smart & Price Wise: Reading Nutrition Facts Labels, & Shopping Cart Check
3. Understanding portion sizes and monitoring tools to keep track
4. MHD diet at home and outside the home: photo of contents of home fridge/contents of cupboard
5. Monthly calls start as tailored to participant using motivational interviewing approach

MHD Diet sessions, components targeted and assessment/monitoring method

Core Session Topic & Learning Objectives	MHD Component Targeted	Biomarker for assessment and/or monitoring method
#1 Key components of MHD Diet Understanding inflammation and role in cognitive health	Embrace foods high in anti-inflammatory properties such as: cantaloupe, broccoli, green leafy vegetables, nuts, berries, beans, whole grains, fish, poultry, other vegetables, fish, water upon waking; seasonings/herbs such as ginger, turmeric, saffron, rosemary, thyme, oregano, cloves; vegetable/bean soups encouraged to increase hydration; choose healthy oils for salads, cooking (e.g. olive oil)	Positive biomarker: Levels of serum B12, tocopherols/ carotenoids (for yellow, orange and green vegetables), levels of metabolized folate (for green leafy vegetables, beans, avocados, bananas, whole grains, fish) , fatty acid panel; Negative biomarkers: C-reactive protein, IL-6
Identifying and preparing foods that reduce inflammation	Limit red meats, butter/stick margarine, cheese, pastries/sweets, fried/fast food	
Hit List		
#2 Shopping Smart: Label Reading at Supermarket	Get to know the produce sections of your supermarket (fresh/frozen/canned); being savvy about nutrition facts labels	Participant brings photo of fridge/cupboard for self-assessment
Hit list	Limit processed foods	
#3: Power of Habits & Self-monitoring	Establish MHD habits and stay hydrated; adapt cooking techniques to add spices/herbs	Participant self-monitors food intake; Participant learns ways to add anti-inflammatory compounds such as herbs/spices in food preparation
Hit list	Limit butter, margarine, pastries, sweets, fast/fried foods, soda, hot dogs, sugar-sweetened beverages	
#4 Dealing skillfully with social situations & food selection	Behavioral strategies to deal with social situations and slips/setbacks	Participant brings photo of fridge/cupboard for self-assessment
Monthly calls to month 18	Tailored to participant using motivational interviewing	Motivational interviewing approach

If assigned to the Usual Diet, participants will:

- continue usual diet
- attend four 2 hr group sessions at Einstein on topics related to aging (8hr)
- receive 16 monthly 20 minute phone calls and/or online program materials on topics related to aging (5 hr, 20 minutes)

5.2 Handling of Study interventions

Session materials and a manual describing the materials will be used for delivering the intervention.

Blinding: Assessment staff for clinic visits (for anthropometry, cognitive testing, etc.) will be blinded to study assignment and participants will be asked not to divulge their randomization status.

5.3 Concomitant Interventions

5.3.1 Allowed interventions

Participants randomized into the study may continue to take medications per primary physician recommendation and should follow their primary physician recommendation re: food allergies, prohibited foods (e.g. participants on blood thinning medications should avoid consuming large amounts of foods high in vitamin K such as green leafy vegetables) if on the Intervention Diet.

5.3.2 Required interventions

Other than the food based anti-inflammatory diet that is eucaloric and the usual diet, no other interventions are required.

5.3.3 Prohibited Interventions

Any intervention that may impact exposure (diet) and outcome (cognition) are prohibited and included in exclusion list. These include the following:

- Participating in any diet or weight loss programs such as: Weight Watchers', Atkins or extreme dieting programs
- Participating in programs to enhance cognition such as playing brain games
- Taking medications that impact cognition such as Aricept, Ritalin and other medications for ADHD.

If participants are prescribed the above medications after randomization or they develop a health outcome that would have made them ineligible to participate in the trial (e.g. diabetes), they will

continue to be followed and the decision to continue in the study will be assessed on a case-by-case basis by investigators with input from the Data Safety Monitoring Board.

5.4 Adherence Assessment

Adherence to intervention:

Attendance and **monthly self-monitoring of three days' intake** will be tracked as process measures to determine participant adherence. Non-adherent participants (as demonstrated by missed sessions or unreachable by phone) will receive up to ten additional phone contacts at different times of day/ day of week. If no contact is established after ten contacts, the participant will be considered as limited contact or no follow-up status. However, each participant will be considered on a case-by-case basis and contact may be established at a later date as determined by participant and study staff.

Adherence to diet via biomarkers: In yr 1-2 we will assess preliminary results of assays in a 5% subsample for carotenoids, tocopherols, and folate. This will serve as a preliminary check for adherence to the intervention. All participant specimens will be analyzed by yr 4-5.

Contamination of Comparison and Intervention: Co-op City encompasses a large area with >50,000 residents and is almost the size of a mini-city; we do not anticipate that there will be much chance for comparison and intervention participants to meet each other as evidenced in our studies (94, 95). We will ask participants to keep their randomization status confidential and request that they not discuss the intervention with other Bronx residents or with their online social networks. Only one member per household will be permitted to be invited to the intervention to preserve independence. If during the course of the study a participant moves out of the Bronx, he/she will be asked to continue the intervention via telephone. Since there are only four visits with the interventionist (that may be completed by phone based on coach's determination) and assessment using the smartphone, moving should not be a barrier to participation.

STUDY PROCEDURES

6.1. Schedule of Evaluations

Assessment	Screening: Phone Assessment	Baseline, Enrollment, R andomiza-tion: Visit 1a (Run- in Visit)	Visit 1b (Baseline)	Visit 2 (W1)	Visit 3 (W2)	Follow-up: Final Visit (W3)
Informed Consent Form	X (oral)	X (written)				
Demographics	X	X		X	X	X
Medical History			X	X	X	X
Cognitive Examination			X	X	X	X
Ambulatory Assessments	X	X	X	X	X	X
Questionnaires		X	X	X	X	
Supplement Use		X	X	X	X	X
Current Medications			X	X	X	X
Blood Chemistries, spot urine			X	X		
Vital Signs & anthropometry: Blood pressure, height, weight, body composition, eye test,			X	X	X	X
Waist/hip circumference						
Inclusion/Exclusion Criteria	X	X				
Enrollment/Randomization			X			
Intervention/Comparison Meetings and Phone Calls			X	X	X	
Adverse Events				X	X	X

6.2 Description of Evaluations

Consenting Procedure

An oral consent is obtained during recruitment when recruiters reach participants by phone and assess eligibility.

Written informed consent is obtained at the first screening visit and will be administered by study staff who have completed required and appropriate IRB training. Recruiters/staff members who will be providing the informed consent will have at least a bachelor's level college degree. Two signed copies (signed by both participant and staff member providing consent) will be obtained. One will be provided to the participant and another copy will be kept in participant file. Bilingual (English/Spanish) consent will be provided as needed. The participant files will be kept in a locked cabinet behind locked doors.

6.2.1 Screening Evaluation

At screening visit #1 participants:

- complete a brief questionnaire,
- receive an explanation of the full study by the study staff
- receive instruction in and have a chance to practice using the smartphone to review activities, mood and play several brief “brain games”
- learn how to use the smartphone to track foods consumed.

At home between the visits (1 hour per day for 2 days)

Beginning the next morning after the visit, participants are asked over two days to:

- complete a review of their activities and mood
- enter food and drink intake using the smartphone
- complete a brief survey when they wake up in the morning and before going to bed
- upon receipt of a signal from the smartphone, play brief brain games several times during the 2 days
- answer follow-up questions by phone about the smartphone or study

Participants should allow about 20 minutes per day for the brain games and 40 minutes for entering your food and drink into the smart phone each day.

Screening Visit 2 (3-5 days after Screening Visit 1, 90 minutes)

During this visit, participants will have to:

- return the smartphone.
- complete questionnaires and exercises that involve memory, attention, vocabulary and response speed.
- They may receive a follow-up phone call to complete a few additional questions.

After this visit, eligibility to continue to the next part of the study will be determined.

6.2.2 Enrollment, Baseline, and Randomization

Enrollment

Participants are considered enrolled in the study after enrollment into one of two study arms.

If deemed to be eligible for the main part of the study, participants are randomly assigned to one of two groups: the Multicultural Healthy Diet group or the Usual or Comparison Diet group.

Baseline Assessments

- blood pressure, blood draw, height, weight, waist/hip circumference, body composition, eye test
- cognitive testing: Dot Memory Task (spatial memory- encoding, distraction, recall), Symbol Search (processing speed), memory binding test or short term memory (to detect early Alzheimer Disease), Operation Span (“letter memory”) & Rotation Span (“arrow memory”), Symmetry Span (“location memory”), Go No-Go to assess working memory, verbal memory and spatial memory; Paired Associates Learning Task (“Shopping List”) that is a test of verbal associative episodic long-term memory. In-Clinic assessments include the STROOP test, NIH Tool Box assessments and self-reported cognitive complaints as described in p. 18-19.

6.2.3 Follow-up visits

Clinic Visit #1 (Scheduled for eligible participants after Screening Visit #2, 2 hr)

At this visit, participants will:

- undergo cognitive testing at the clinic
- respond to questionnaires about medical history, moods & daily experiences
- receive randomization assignment to Usual Diet or Multicultural Healthy Diet
- schedule a 30 minute visit for eye test and body measurements: blood pressure, blood draw, spot urine collection, height, weight, waist/hip circumference, body composition.

At home after Visit #1 (1 hour per day for 7 days)

Participants are asked to do the following over the next seven days:

- enter food intake using the smartphone
- complete a brief survey when waking up in the morning and before going to bed
- play brief brain games four times during the day
- at the end of the 7 days, return the smartphone to the clinic after completing the exercises

Randomization

Randomization occurs after Clinic Visit #1 (Baseline) when body measurements are complete. When adequate numbers of participants (about 8-10) are randomized to start a comparison or intervention group, participants will be invited to the sessions. In the meantime they will receive informational materials about the study in preparation for the sessions.

Clinic Visit #2 (Scheduled 9 months after Visit #1, 2 hr)

This visit is identical to Visit #1.

At home after Visit #2 (1 hour per day for 7 days)

These activities are identical to at-home activities after Visit #1.

Clinic Visit #3 (Scheduled 9 months after Visit #2, 2 hr)

This visit is identical to Visit #1, except that there will be no blood tests or urine collection scheduled after the visit.

At home after Visit #3 (1 hour per day for 7 days)

These activities are identical to at-home activities after Visit #1.

Clinic Visit #4 (Scheduled 9 months after Visit #3, 2 hr)

This visit is identical to Visit #1, except that there will be no blood tests or urine collection scheduled after the visit.

At home after Visit #4 (1 hour per day for 7 days)

These activities are identical to at-home activities after Visit #1.

6.2.4 Completion/Final Evaluation

The final visit is Clinic Visit #4 after which the smartphones are returned to the clinic and study ends.

7. SAFETY ASSESSMENTS

Since participants are changing their diets from one that is pro-inflammatory to one that is anti-inflammatory, they will be asked to consume fruits/vegetables, legumes, nuts, fish, whole grains and other anti-inflammatory food components such as scallions or chives and other herbs and spices to their diet and reduce intake of processed and fried foods, sweets and foods high in saturated fats. They also need to make sure they are hydrated, especially upon waking up.

Participants will be screened for being on any diets that could preclude consumption of the MHD such as allergies that would make it difficult to stay on this dietary pattern. It is likely that

participants will see a benefit from consuming the MHD. These beneficial effects could include decrease in constipation, higher energy level. Participants will be asked to report any new developments related to their consumption of the MHD. If participants developed a medical issue that precludes continuation in the study, they may withdraw from the study.

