7.2 Methods and Timing for Assessing, Recording, and Analyzing Safety Parameters

The MHD for healthy participants- the target of this study- is generally safe. Should participants develop health problems during the study that precludes staying on this diet (e.g. unintentional weight loss, eating disorders), the participants are advised to contact primary physician and decide the merits of continuing in the study and are free to discontinue participation. Participants are asked to report any such developments.

7.3 Adverse Events and Serious Adverse Events.

An adverse event (AE) is generally defined as any unfavorable and unintended diagnosis, symptom, sign (including an abnormal laboratory finding), syndrome or disease which either occurs during the study, having been absent at baseline, or if present at baseline, appears to worsen. Adverse events are recorded regardless of their relationship to the study intervention.

A serious adverse event (SAE) is generally defined as any untoward medical occurrence that results in death, is life threatening, requires inpatient hospitalization or prolongation of existing hospitalization, results in persistent or significant disability/incapacity, or is a congenital anomaly.

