9.3 Interim analysis and Stopping Rules

The study will be stopped for reasons of poor study performance such as slow accrual, high losses to follow-up or poor quality control.

While the possibility of this event is very low, should there be need to suspend the study due to safety issues such as high number of SAEs overall, the number of occurrences of a particular type of SAE, severe AEs/reactions, or increased frequency of events. Such findings are presented to the study statistician or to the Data and Safety Monitoring Board (DSMB) statistician to review the events by group to determine whether there are statistical as well as clinical concerns. The statistician reports his findings to a closed session of the DSMB or to the Safety Officer and/or NIA. The findings are used to determine what steps will be taken.

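### Outside the scheduled visits, the only stated requests to report health developments are tied to the MHD, so non-serious adverse events may be captured unequally and the by-group safety review is open to ascertainment bias

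*Protocol*

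**What the plan says.** Protocol section 7 (Safety Assessments) describes participants who are changing their diet and then says: "Participants will be asked to report any new developments related to their consumption of the MHD". Section 7.2, whose title promises methods and timing, begins its only reporting instruction with "Should participants develop health problems during the study that precludes staying on this diet" and ends it with "Participants are asked to report any such developments". Neither section gives a timetable, a form or a contact route.

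The recording rule in section 7.3 is wider: "Adverse events are recorded regardless of their relationship to the study intervention". In the schedule (section 6.1), the row "Adverse Events" is marked at Visit 2, Visit 3 and the final visit only, for both arms.

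Between visits, section 5.1 gives each arm four group sessions and 16 monthly calls. The diet arm's calls are about following the diet. Comparison participants "receive 16 monthly 20 minute phone calls and/or online program materials on topics related to aging". Different coaches serve the two arms (section 3, Training of Coaches).

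Under section 9.3, if a safety concern arises, the findings go to a statistician "to review the events by group to determine whether there are statistical as well as clinical concerns", and the result determines the next steps. The listed concerns include serious events, severe events and a rise in event frequency. No numerical boundary is given. The SAP plans no adverse-event analysis by arm; its Introduction says only that the study team and the DSMB monitor safety.

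**The concern.** A comparison of event frequency between arms is fair only if an event has the same chance of being recorded in each. Here the recording rule covers every event, but the stated requests cover only those connected with the MHD. A comparison participant on a usual diet has no MHD to link an event to. On the visible text, that participant's first stated prompt is the next visit, up to nine months later.

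The by-group review in section 9.3 is the only arm comparison of safety in either document, and it can lead to the study being suspended. If capture differs by arm, the review measures opportunity to report as well as risk. Minor events in both arms may also be forgotten or found late.

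**Working it through.** The documents give no adverse-event rate, safety alpha or stopping boundary, so there is no stated figure to reproduce. The check has two parts.

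**1. Routes of capture, by arm**

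| Route | MHD arm | Comparison arm |
|---|---|---|
| Scheduled enquiry (section 6.1) | Months 9, 18, 27 | Months 9, 18, 27 |
| Visit assessment staff (section 5.2) | Blinded | Blinded |
| Planned sessions and calls (section 5.1) | 4 + 16 = 20 | 4 + 16 = 20 |
| Stated adverse-event question on those contacts | None | None |
| Stated request to report otherwise (sections 7, 7.2) | Developments tied to the MHD | None stated |
| Serious events (section 7.4) | Reported on discovery, related or not | Same |

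Scheduled enquiry and contact frequency match. The stated difference lies in what participants are asked to report outside the scheduled enquiry.

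**2. How much unequal capture could matter (assumed values)**

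From the protocol: 145 per arm and three nine-month intervals. Assumed: equal true rates of 0.5 events per person per interval, no attrition, Poisson counts and a two-sided 5% test. Visit enquiry captures a fraction r. Spontaneous reporting recovers a further fraction of the remainder, sD in the diet arm and sC in the comparison arm.

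- True events per arm: N = 145 × 0.5 × 3 = 217.5
- Recorded: XD = N[r + (1 − r)sD]; XC = N[r + (1 − r)sC]
- Apparent ratio: XD/XC
- z = (XD − XC)/√(XD + XC)
- Probability of a flag: Φ(z − 1.96) + Φ(−z − 1.96)

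| r | sD | sC | Recorded, diet vs comparison | Ratio | z | Flagged |
|---|---|---|---|---|---|---|
| 0.7 | 0.1 | 0 | 159 vs 152 | 1.04 | 0.37 | 7% |
| 0.5 | 0.2 | 0 | 131 vs 109 | 1.20 | 1.41 | 29% |
| 0.5 | 0.3 | 0 | 141 vs 109 | 1.30 | 2.06 | 54% |
| 0.4 | 0.4 | 0 | 139 vs 87 | 1.60 | 3.47 | 93% |
| 0.5 | 0.3 | 0.2 | 141 vs 131 | 1.08 | 0.66 | 10% |
| 0.5 | 0.06 | 0 | 115 vs 109 | 1.06 | 0.44 | 7% |
| 0.5 | 0.2 | 0.3 | 131 vs 141 | 0.92 | −0.66 | 10% |

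The first four rows allow no spontaneous reporting in the comparison arm. The fifth allows some. In the sixth, only 20% of missed events are diet-related, so sD = 0.2 × 0.3 = 0.06. The seventh reverses the direction. With equal capture the expected ratio is 1.00 and the test flags at its nominal 5%.

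**The case against.** A reader might infer that only the diet arm is asked to report between visits. The documents do not say so. The requests use the general word for participants and give no timing, and silence about the comparison arm is not an instruction to it. The consent forms, the Manual of Procedures and any text between sections 7.5 and 8 were not available to us and may contain a neutral request. The point is therefore limited to the visible text.

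Several provisions apply to both arms. Medical history and current medications are collected at Visits 2 to 4 (section 6.1). Abnormal findings at visits are documented and reviewed by a physician (section 7.1). Section 5.3.3 covers health problems that would have made a participant ineligible, and section 8 covers weight loss and other health issues; neither names an arm. Serious events are reported on discovery whatever their cause (section 7.4). These limit the problem, chiefly for serious events and for whatever the visits uncover. They do not supply a neutral request to report non-serious events between visits. Discovery of a serious event can also be delayed if nobody asks.

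A reader might also infer that the diet will look harmful. That direction is not established. The comparison sessions (section 3) include the bodily complaints of ageing and eye health, taken by a general health coach, and could prompt symptom reports at least as readily as diet coaching.

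Finally, section 9.3 applies no 5% test. The review follows a safety concern, weighs clinical as well as statistical evidence, and goes to a closed DSMB session, the Safety Officer and/or the NIA. An imbalance in counts does not automatically suspend the study. That is correct, and it means that no formal error rate can be attached to the review.

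**Conclusion.** The point holds in a limited form. On the visible text, the requests to report outside the month 9, 18 and 27 enquiries are tied to the MHD, and no arm-neutral question is stated for the sessions or calls. This sits badly with the rule that all events are recorded regardless of relationship. Non-serious events may be captured unequally, so the section 9.3 review is open to ascertainment bias. To say that it is biased, or biased against the diet, would go beyond the documents.

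The size is unknown. With comparison-arm spontaneous reporting set to zero, the illustration runs from about 7% to 93%. A figure such as 54% should not be read as the trial's false-alarm rate: changing only the comparison arm's spontaneous fraction from 0 to 0.2 brings it to about 10%. The illustration also ignores attrition, although section 3 reports 260 of 290 randomised participants at Visit 2. It shows only that modest unequal capture can range from trivial to important. This is a low-cost improvement to the safety comparison and does not affect the primary cognitive analysis.

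**What to change.** 1. Reword the reporting requests in sections 7 and 7.2 so that all participants in both arms are asked to report any new or worsened health problem. The rest of those sections can stay as written.
2. Use one identical scripted question in both arms at Visits 2 to 4 and on the existing monthly calls, and add it to the section 6.1 schedule. If the Manual of Procedures already has such a question, cite it.
3. Record how each event was captured: visit, call or spontaneous report.
4. State in section 9.3 that the by-group review rests primarily on events solicited identically at visits by blinded staff, with call and spontaneous reports shown separately by arm.

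Section 3 already reports randomisation and Visit 2 retention as past events. If follow-up is complete, classify the existing events by source and make the arm comparison on visit-solicited events.

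The cost is protocol wording, one form field and roughly a minute per existing call, with no new contacts or procedures. There are three downsides. More minor events will be logged. Call reports will be taken by coaches who know the arm, which a script may reduce but cannot remove. Call coverage is also imperfect: calls stop at month 18, so months 18 to 27 rely on visits in both arms; online materials may replace calls; and merging up to three sessions into one call is stated only for the MHD arm. For these reasons call reports should not be the sole basis of the comparison.
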